2.3. Benefit/Risk Assessment

Summaries of findings from both clinical and non-clinical studies conducted with oral and CAB LA or RPV LA can be found in the current Investigator's Brochures.

Oral RPV is an approved medicinal product and detailed information on its benefit/risk profile together with any risk mitigation measures are described in product labelling. (Current Edurant Prescribing Information)

2.3.1. Oral CAB and CAB LA (GSK1265744/GSK1265744 LA)

Since CAB Exposure in humans with and without HIV infection is limited, the clinical safety profile in humans has yet to be fully elucidated. The following risks have primarily been identified during routine preclinical testing and/or from the clinical trial experience to date and are considered of potential relevance to clinical usage in the context of this protocol. Additional information about the clinical experience to date and possible risks associated with treatment using CAB can be found in the Summary of Data and Guidance for the Investigator section of the investigator's brochure (IB).

Potential Risk of Clinical Significance	Summary of Data/Rationale for Risk	Mitigation Strategy
Drug Induced Liver Injury (DILI)	Less than 1% of participants in the CAB program to date have developed transaminitis (elevated liver transaminases characterized by predominant alanine aminotransferase (ALT) elevation). In most participants, transient transaminitis was explained by acute hepatitis C infection (majority) and other systemic infections. In a small number of participants, there was not an alternative explanation, suggesting a mild form of drug induced liver injury (DILI) without hepatic dysfunction, which resolved upon withdrawal of treatment with CAB.	 Exclusion criteria as described in Section 5.2 will prohibit participation of PLHIV who have significant liver impairment based on screening liver chemistry including transaminases (ALT and aspartate aminotransferase [AST]) as well on prior medical history. Participants with a history of chronic liver disease with ongoing inflammation and/or fibrosis will have additional confirmatory assessments to confirm suitability for entry into the study. Liver transaminases (ALT and AST) will be monitored throughout this study and the liver chemistry stopping criteria will be adopted as described in Section 7.1, Section 10.6.2, and Section 10.6.5 of this protocol. Participants will be withdrawn from CAB treatment where no compelling alternative cause is identified and DILI is suspected.
Injection Site Reactions (ISRs)	Clinical experience to date has demonstrated ISRs occur in the majority of exposed participants treated with CAB LA but are generally mild (Grade 1) or moderate (Grade 2) and include events of pain, tenderness, erythema, or nodule formation of several days duration (median duration for individual events <1 week). ISRs may occur more than once in an individual participant receiving multiple injections. Although some Grade 3 ISRs have	Administration advice will be given to minimize risk of poor administration technique giving rise to injection site reactions. Advice on care, monitoring, natural course, and treatment of ISRs is given in study documentation. Advice will be given to participants on care of injection site on day/days immediately post administration, use of analgesia, compresses where appropriate.

Potential Risk of Clinical Significance	Summary of Data/Rationale for Risk	Mitigation Strategy
	been reported, overall ISRs appear tolerable and have not to date been associated with an excess of participants' withdrawal.	Participants will be closely monitored for ISRs particularly for signs of pain, tenderness, infections, erythema, swelling, induration, or nodules (granulomas or cysts) throughout the study.
		Complications of ISRs such as infections (abscess, cellulitis) and collections of fluid requiring drainage will be monitored Significant ISRs may be photographed and referred to a dermatologist for specialist advice.
Hypersensitivity Reactions (HSR)	Hypersensitivity reactions have been reported as uncommon occurrences with integrase inhibitors (INI), including the closely related compound dolutegravir, and were characterized by rash, constitutional findings, and sometimes, organ dysfunction, including liver injury.	The risk of developing a hypersensitivity reaction post administration of IM CAB will be minimized by the use of a 4-week oral lead-in of oral CAB to determine individual safety and tolerability prior to the introduction of IM CAB.
	While there have been no clinical cases of hypersensitivity to CAB to date, there is a theoretical risk of systemic or severe hypersensitivity reactions with or without hepatic symptoms associated with use of IM CAB. The long exposures anticipated	Clinical assessments, laboratory tests (including liver transaminases) and vital signs will be performed throughout this study. Results from these assessments may aid early detection of HSR.
	after IM CAB injection may complicate the management of a drug hypersensitivity reaction, were it to occur.	Oral CAB will be withdrawn immediately for cases with suspected HSR during the oral CAB lead-in phase and would not proceed to the injection phase. Participants receiving the injection who develop suspected HSR would not receive further injections. During oral (oral bridge) and IM CAB treatment, any HSR reactions that occur would be managed supportively.

Potential Risk of Clinical Significance	Summary of Data/Rationale for Risk	Mitigation Strategy
Effects in pregnancy seen in nonclinical studies	In animal reproduction studies, CAB when administered to rats at > 30 times the systemic exposure at the maximum recommended oral human dose (MRHD) of 30 mg during organogenesis through delivery, had adverse effects on labor and delivery that may be related to a delay in the onset of parturition, resulting in increased fetal mortality (stillbirths) and neonatal deaths immediately after birth. A delay in the onset of parturition, increased stillbirths and neonatal deaths were observed in a rat pre- and postnatal development study at greater than 28 times the exposure at the recommended human dose (RHD). No evidence of adverse developmental outcomes was observed with oral cabotegravir in rats or rabbits (greater than 28 times or similar to the exposure at the RHD, respectively) given during organogenesis. The clinical significance of these finding in humans is unknown. For pregnant participants remaining in the study, refer to Appendix 15 for additional data regarding CAB and pregnancy. Female participants on LA dosing who become pregnant will have exposures throughout pregnancy due to the long half-life and PK tail of CAB/RPV. Pregnant participants who are withdrawn from study and are initiated on an alternative oral ART regimen consisting of either 2 or 3 antiretrovirals to protect the life of the mother and for the prevention of MTCT, potentially expose the fetus to additional ARVs during gestation (in some cases upwards of 5 antiretrovirals).	 Pregnant females are excluded from enrollment in this study and women of childbearing potential (WOCBP) are required to adopt highly reliable means of contraception during participation, and throughout the long term follow up phase of this study following exposure to CAB LA. WOCBP are also required to undergo regular pregnancy testing throughout study conduct. Pregnant participants who remain in the study do not need pregnancy testing for the duration of the pregnant during the study may remain in the study provided all protocol defined pregnancy related assessments, procedures and documentation are completed, and a pregnancy specific ICF addendum is signed by the participants are found in Appendix 15
Potential effects in women exposed to dolutegravir during	A preliminary analysis of an ongoing birth outcome surveillance study in Botswana involving women exposed to dolutegravir (DTG), a different molecule in the same integrase class of	• Pregnant females are excluded from enrollment in clinical trials of CAB at this time and women of childbearing potential (WOCBP) are required to adopt

Potential Risk of Clinical Significance	Summary of Data/Rationale for Risk	Mitigation Strategy
conception and early pregnancy	medications as CAB, identified four cases (as of May 2018) of neural tube defects in 426 infants born to mothers who were exposed to DTG-containing regimens from the time of conception. In the same study, no infant born to a woman who started DTG during pregnancy had a neural tube defect, out of 2,824 women. A causal relationship of these events to the use of DTG has not been established. The incidence of neural tube defects in the general population ranges from 0.5-1 case per 1,000 live births. As neural tube defects occur within the first 4 weeks of fetal development (at which time the neural tubes are sealed) this potential risk would concern women exposed to DTG at the time of conception and in early pregnancy. Recently updated data (April 2020) for this birth outcome study showed that among women who were on DTG when they became pregnant, 7/3591 neural tube defects (NTD) occurred (0.19%). In comparison, NTDs were identified in 21/19,361 (0.11%) women delivering on any non-DTG antiretrovirals. There was not a significant difference in the number of neural tube defects between births to women taking DTG and those taking other non-DTG antiretroviral treatments (0.09% difference). The clinical relevance of either of these findings in relation to CAB use is unknown	 highly reliable means of contraception during participation and throughout long term follow up phases of studies after exposure to CAB LA. WOCBP also undergo regular pregnancy testing throughout study conduct. Pregnant participants who remain in the study do not need pregnancy testing for the duration of the pregnancy. It should be noted that CAB concentration could remain for prolonged periods despite discontinuation of CAB LA Participants who become pregnant during the study may remain in the study, provided all protocol defined pregnancy related assessments, procedures and documentation are completed and a pregnancy specific ICF addendum is signed by the participant. Details regarding management of pregnant participants is found in Appendix 15.

Potential Risk of Clinical Significance	Summary of Data/Rationale for Risk	Mitigation Strategy
Development of Resistance following discontinuation of CAB LA	Residual concentrations of CAB would remain in the systemic circulation of participants who stop CAB LA treatment for prolonged periods (more than 1 year, in some participants after last injection (e.g., for tolerability issues or treatment failure). Participants discontinuing CAB LA regimen may be at risk for developing HIV-1 resistance to CAB many weeks after discontinuing injectable therapy.	After participants stop CAB LA, oral highly active antiretroviral therapy (HAART) regimens will be prescribed within 1 month (-7 days) after the last Q1M dose or within 2 months (±7 days) after the last Q2M dose, and following consultation with the Medical Monitor. This would be anticipated to result in continued suppression or rapid re-suppression of HIV-1 RNA thus minimizing the risk of emergent resistance. The Sponsor will continue to monitor participants in this study who discontinue the LA regimen prior to local availability of CAB LA+ RPV LA for a minimum of 52 weeks from the time of the last LA administration. Post- commercial local availability, the Sponsor will continue to monitor participants in this study who prematurely discontinue a LA regimen for safety reasons for a minimum of 52 weeks from the time of the last LA administration.
Drug-Drug Interactions (DDIs)	 For a complete listing of permitted and prohibited concurrent medications for CAB and CAB LA, refer to Section 6.6 CAB and CAB LA should not be co-administered with the following medicinal products, as significant decreases in CAB plasma concentrations may occur (due to UDP-glucuronosyltransferase (UGT) enzyme induction), which may result in loss of therapeutic effect of CAB. the anticonvulsants carbamazepine, oxcarbazepine, phenobarbital, phenytoin 	All participants will be informed of prohibited medications throughout the study and updates provided as needed via the informed consent.

Potential Risk of Clinical Significance	Summary of Data/Rationale for Risk	Mitigation Strategy
Inadvertent intravenous injection (accidental	 the antimycobacterials rifampicin, rifapentine, rifabutin St John's wort (Hypericum perforatum) Oral CAB administration only: Antacid products containing divalent cations (e.g., aluminum, calcium, and magnesium) must be taken at least 2 hours before or at least 4 hours after CAB. Participants discontinuing a LA regimen may be at risk for developing drug-drug interactions (DDIs) many weeks after discontinuing injectable therapy. As with any intramuscular injection, it is possible that CAB LA can be inadvertently administered intravenously instead of intramuscularly possibly resulting in higher than expected 	Training will be provided to all sites on proper injection technique.
maladministration)	 concentrations of CAB shortly after injection and lower concentrations thereafter. This could be due to administrator error, improper injection technique and / or improper needle length used based on body type. The clinical consequences of overdose with CAB LA are currently unknown. HIV-1 viral suppression may not be effective following accidental maladministration. 	 Should IM maladministration be suspected at any time (e.g. suspected under or overdose or inadvertent IV dosing), a post dose electrocardiogram (ECG), vital signs, or any other supportive testing may be obtained at the discretion of the investigator, and the Medical Monitor will be notified. Laboratory samples for safety parameters and HIV-1 RNA will be closely monitored in all participants. Additionally, an unscheduled PK sample may be drawn approximately 2 hours post dosing for future evaluation of CAB concentrations.

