All patient study participants will complete the screening phase of up to 35 days prior to enrollment. Participants may be re-screened once. Participants who are enrolled into the trial and subsequently withdrawn from the study, for any reason, may not be re-screened. Participants may be enrolled as soon as all eligibility requirements have been confirmed at the site. Informed consent must be obtained prior to any study procedures for patient study participants, including any screening assessment.

HIV-1 infected participants who meet all eligibility criteria will be switched from their pre-baseline regimen to an oral regimen (CAB 30 mg + RPV 25 mg once daily) during the oral lead-in phase. Participants will return to the clinic, and if laboratory and clinical evaluations continue to support progression into the LA portion of the study, will take the last dose of their oral regimen (CAB 30 mg + RPV 25 mg) and receive the first dose of CAB LA (600 mg) + RPV LA (900 mg) injections on the same day (Month 1). The participant will receive the second injections CAB LA (600 mg) + RPV LA (900 mg) one month later (Month 2). All subsequent injections will occur every two months thereafter (Month 4, Month 6, etc). The total length of the treatment phase is approximately one year.

Note: Patient study participants with \geq Grade 1 LFTs at screening and or day 1 must be discussed with the Medical Monitor prior to initiation of LA dosing; continuation in the study or progression onto LA dosing may require additional evaluations, including labs drawn after a period of oral dosing with CAB + RPV.

The dosing window for the second injections will be +0/-7 days from the projected target date (target date is established at Month 1). All subsequent injection windows (starting with Dose 3) will be +7/-7 days from the projected target date. Doses outside of the window *may* be allowed with prior Medical Monitor approval.

Participants will continue CAB LA + RPV LA until:

- They have completed the study (reached dose 7, Month 12) and the intervention is locally approved and available for the Investigator to prescribe
- the participant no longer derives clinical benefit
- the participant meets a protocol-defined reason for discontinuation
- the development of CAB LA and/or RPV LA is terminated
- participant withdraws consent
- participant is withdrawn due to investigator discretion
- participant is withdrawn due to participant or investigator non-compliance

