10.6.2. Grade 1 or Grade 2 Toxicity/Adverse Event

Participants who develop a Grade 1 or Grade 2 AE or toxicity may continue IP at the discretion of the Investigator. (NOTE: See Section 10.6 Specific Toxicities/Adverse Event Management" for exceptions to this guideline). Participants who choose to withdraw from study due to a Grade 1 or 2 AE should have study withdrawal and followup evaluations completed.

Participants who develop ALT ≥3 times ULN while on study must consult with Medical Monitor prior to starting or continuing of CAB LA and RPV LA.

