However, if the etiology of the rash has been definitively diagnosed as being unrelated to study drug and due to a specific medical event or a concomitant infection or a concomitant non-study medication, routine management should be performed and documentation of the diagnosis provided. In this situation, the study drug should be continued.

Participants in the Follow-Up Phase who are receiving ABC as part of their regimen should be evaluated for the possibility of a clinically suspected ABC HSR and managed appropriately as outlined in the local prescribing information for ABC.

Any participant receiving at least one dose of CAB LA and /or RPV LA who discontinue IP / Withdraw will initiate treatment with HAART and enter the LTFU phase for 52 weeks of follow-up.

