10.6.5.9. Allergic reaction

Participants may continue study drug for Grade 1 or 2 allergic reactions at the discretion of the Investigator. The participant should be advised to contact the Investigator immediately if there is any worsening of symptoms or if further systemic signs or symptoms develop. Antihistamines, topical corticosteroids, or antipruritic agents may be prescribed.

Participants with Grade \geq 3 allergic reactions that are considered to be possibly or probably related to the study drug should permanently discontinue the CAB LA + RPV LA regimen and the participant should be withdrawn from the study. Participants should be treated as clinically appropriate and followed until resolution of the AE.

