10.6.5.10. Rash Without HSR Symptoms

Including serious skin reactions such as Stevens-Johnson Syndrome, Toxic Epidermal Necrolysis, Erythema Multiforme or rash with significant liver dysfunction.

Participants should be instructed to contact the Investigator as soon as possible if they develop a rash on study.

As many products also cause rash and/or serious skin reactions, all other medicinal products that the participant is receiving should also be reviewed and discontinued as appropriate.

The following guidance is provided for clinical management of participants who experience rash alone in the absence of systemic or allergic symptoms or signs of mucosal or target lesions.

CAB is an analogue of DTG and mild to moderate rash is an expected adverse reaction for DTG-containing ART. Episodes generally occur within the first 10 weeks of

treatment, rarely require interruptions or discontinuations of therapy and tend to resolve within two to three weeks. No instances of serious skin reaction, including SJS, TEN and erythema multiforme, have been reported for DTG in clinical trials. For further characterization of HSR and rash observed with DTG-containing ART, please see the current version of the CAB IB. Rash is an adverse drug reaction (ADR) for RPV. In clinical trials, most rashes emerged during the first 4 weeks of treatment, were transient, and usually mild (Grade 1) to moderate (Grade 2). There were no Grade 4 rashes and none were serious. Treatment related Grade 3 rash was reported in 0.1% of participants in the RPV group. Treatment related rash led to permanent discontinuation in 0.1% of participants in the RPV group. No cases of erythema multiforme, SJS or TEN have been reported during clinical development of RPV.

Participants with an isolated Grade 1 rash may continue study drug at the Investigator's discretion. The participant should be advised to contact the Investigator immediately if there is any worsening of the rash, if any systemic signs or symptoms appear, or if mucosal involvement develops.

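### Section 10.6.5.9 leaves Grade 1-2 allergic reactions to investigator discretion without excepting suspected HSR, for which Section 2.3.1 stops dosing at any grade

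*Protocol*

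**What the plan says.** The hypersensitivity row of the CAB risk table (Protocol Section 2.3.1) has three instructions. In the lead-in, "Oral CAB will be withdrawn immediately for cases with suspected HSR during the oral CAB lead-in phase", and the participant does not go on to injections. In the injection phase, "Participants receiving the injection who develop suspected HSR would not receive further injections". Then, "During oral (oral bridge) and IM CAB treatment, any HSR reactions that occur would be managed supportively". None of these mentions grade.

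Appendix 6 (Section 10.6, Toxicity Management) works by grade. Section 10.6.2 states that "Participants who develop a Grade 1 or Grade 2 AE or toxicity may continue IP at the discretion of the Investigator" and sends the reader to the specific-toxicity text for exceptions. Section 10.6.5.9, on allergic reactions, repeats the discretion: "Participants may continue study drug for Grade 1 or 2 allergic reactions at the discretion of the Investigator". It makes permanent discontinuation mandatory only at Grade 3 or above, and then only if the reaction is possibly or probably related to study drug. It contains no exception for suspected HSR and no reference to Section 2.3.1.

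The neighbouring Section 10.6.5.10 is limited to "rash alone in the absence of systemic or allergic symptoms or signs of mucosal or target lesions". The one instruction in Appendix 6 about suspected HSR is in Section 10.6.4 and concerns abacavir: participants taking it during follow-up "should be evaluated for the possibility of a clinically suspected ABC HSR".

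**The concern.** For the same participant, one section removes a discretion that another grants. Section 10.6.5.9 is the operative guidance for an allergic reaction. A site that follows it and continues dosing after a Grade 1-2 reaction in which HSR is suspected would breach Section 2.3.1 with no warning on the page it was using.

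The stake is an injection given when the protocol meant none to be given. Section 2.3.1 notes that the long exposure after injection could make a hypersensitivity reaction harder to manage, and presents the oral lead-in as the way to reduce that risk. Section 6.5.3 says both long-acting drugs may remain detectable in plasma for over a year. The point concerns participant safety and site compliance. It does not touch the analysis.

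**Working it through.** No figure in the plan is in dispute, so the check is a comparison of rules followed by a rough count.

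**Step 1: which rules stop a suspected HSR?**

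| Rule | Triggered by | Catches Grade 1-2 suspected HSR? |
|---|---|---|
| Section 2.3.1 | Suspected HSR in lead-in or injection phase | Yes, any grade |
| Section 7, mandatory list | Rash Grade 3 or higher, or Grade 2 with systemic involvement, no compelling other cause | Only Grade 2 rash with systemic signs |
| Section 10.6.5.10 | Rash Grade 2 or higher with an ALT increase | Only with both |
| Section 10.3.1 | ALT at least 3x ULN (3x baseline if baseline ALT exceeds 1.5x ULN) with symptoms attributed to liver injury or hypersensitivity | Only with that ALT rise |
| Section 10.6.5.9 | Allergic reaction Grade 3 or higher, possibly or probably related | No; Grade 1-2 left to discretion |
| Section 7.1 | Any protocol-defined withdrawal criterion | Yes, if Section 2.3.1 is read as one |

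**Step 2: a test case.** Take a Grade 1 rash with fever and normal ALT, which the investigator suspects is HSR to CAB. Section 2.3.1 describes integrase-inhibitor HSR as skin and general symptoms with organ involvement only in some cases, and says the theoretical CAB risk may or may not include hepatic symptoms, so the case fits.

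- Section 7 rash criterion: not met (Grade 1).
- Section 10.6.5.10 ALT rule: not met (Grade 1, normal ALT).
- Section 10.3.1: not met (normal ALT).
- Section 10.6.5.9: may continue, at discretion.
- Section 2.3.1: stop.

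The direct rules give two answers. Only reading Section 2.3.1 as the narrower rule, or bringing it in through Section 7.1, settles the matter.

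**Step 3: the check before the first injection.** The Synopsis makes the first injection conditional: "if laboratory and clinical evaluations continue to support progression into the LA portion of the study". Section 4.3.3 has the same condition. This should stop most lead-in cases, but it governs entry to injections, not later doses.

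**Step 4: size.** The documents give no HSR rate; Section 2.3.1 reports no clinical cases of hypersensitivity to CAB so far. Planned enrolment is 474 (Section 9.2). The range 0% to 0.5% for any suspected HSR is an assumption:

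- 0% x 474 = 0
- 0.5% x 474 = 2.37, about 2.4

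The residual gap is a subset of that count. For scale only, Section 10.6.5.10 gives 0.1% permanent discontinuation for treatment-related rash with RPV: 0.1% x 474 = 0.47, about half a participant. That is rash, not HSR.

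**The case against.** The strongest defence is that nothing conflicts. Section 10.6.5.9 permits continuation but does not order it; Section 2.3.1 is a narrower prohibition, and a site obeys both by stopping. Section 7.1 turns any protocol-defined withdrawal criterion into a mandatory stop, and Section 2.3.1 can fairly be read as one. This stands as a way to reconcile the text, and it keeps the severity low. It does not withdraw the written permission in 10.6.5.9, and the site has to work the reconciliation out unaided.

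A second defence is that an allergic reaction and HSR are different things. The protocol does not separate them, and Section 10.6.5.9 speaks of further systemic signs, which suggests some may already be present. The SAP's hypersensitivity grouping (Section 13.9.3) draws partly on allergic-condition terms, but it is a tabulation list and only weak support for overlap. The Investigator's Brochure may say more; it is not among the documents.

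A third defence is that the gap is nearly empty. That is largely right. The rash and liver rules cover much of the HSR picture. In addition, the RPV rash row of Section 2.3.2 asks for close attention to systemic signs in every rash, and exclusion criterion 18 keeps out people with known allergy to these drugs or their class.

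Three stronger readings do not hold:

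- A reader might infer that the protocol tells sites to inject despite suspected HSR. It does not; it leaves a discretion unqualified.
- A reader might infer from the mandatory list in Section 7 that suspected HSR is not a stopping reason. That list is not exhaustive: Sections 10.6.5.9 and 10.6.5.10 contain further mandatory stops.
- A reader might infer that the rule covers HSR to RPV, or that Section 2.3.1 orders RPV withdrawn. It is a CAB rule, and the RPV risk table in Section 2.3.2 has a rash row but no HSR row.

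**Conclusion.** The inconsistency is real and of low severity. Section 2.3.1 stops dosing for suspected HSR in the lead-in and injection phases whatever the grade; Section 10.6.5.9 leaves Grade 1-2 allergic reactions to discretion and does not except that case. The remaining gap, after the safeguards above, is Grade 1-2 suspected HSR with neither a Grade 2 rash with systemic involvement nor a qualifying ALT rise. It should affect very few participants, possibly none. The count rests on the assumed rate of 0% to 0.5%; the conclusion rests on an allergic reaction and a suspected HSR being able to be the same event. No endpoint, sample size or power statement is affected. The change is justified by low cost and by the irreversibility of an injection given in error, not by expected numbers.

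**What to change.** In the first sentence of Section 10.6.5.9, after the reference to investigator discretion, add:

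> , except where HSR to CAB is suspected, in which case Section 2.3.1 applies regardless of grade (oral lead-in CAB is withdrawn and the participant does not proceed to injection, or receives no further injections); other antiretrovirals are handled per Section 10.6.1

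The clause names CAB because Section 2.3.1 is a CAB rule. It sends the other drugs to Section 10.6.1, which requires all antiretrovirals to be held if one is held for toxicity; that section concerns holding, so the clause should not be read as ordering permanent RPV withdrawal under Section 2.3.1. The Section 2.3.1 text on supportive management, including during oral bridging, stays as it is, as does the Grade 3-and-above sentence of 10.6.5.9. No addition to the Section 7 list is needed; a bullet there could widen the stopping criteria.

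Cost: one clause and a note to sites. No new procedures, data or SAP changes.
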